**Table 1. Study measures for PrEP-PP for AIM 1**

Primary Outcomes	Measurement	Source	Frequency
PrEP initiation	# of women who initiate PrEP over time / total # of women in active cohort = proportion of women who initiate PrEP	Electronic provider log (REDCap)	Quarterly
PrEP continuation	# of women on PrEP who return for study visits (do not miss more than 1 visit) / total # of women in active cohort who are prescribed PrEP= proportion of women on PrEP who continue in PrEP study	Electronic provider log (REDCap)	Quarterly
PrEP persistence (subjective)	# of women reporting taking PrEP in $\geq 5$ out of last 7 days or $\geq 25$ out of last 30 days (self-reported)/ total woman-time on PrEP in active cohort = PrEP persistence rate (subjective)	Electronic provider log (REDCap)	Quarterly
PrEP persistence (objective)	# of women taking PrEP who have $\geq 600$ fmol/punch (~7 doses/week) from DBS TDF-DP at 3rd trimester, delivery, and 6 weeks postpartum (and during sexual risk periods during that time) / total woman-time on PrEP in active cohort = PrEP persistence rate (objective)	Lab analysis of TDF-DP measures	Yearly and end of study
Secondary Outcomes			
Prevention effective persistence	4. # of women reporting adherence to PrEP (as per PrEP persistence subjective measure)/ total woman-time reporting sexual activity in past 30 days	Electronic provider log (REDCap)	Quarterly
	5. # of women having TDF-DP in DBS (as per PrEP persistence objective measure)/ total woman-time reporting sexual activity in past 30 days	Lab analysis of TDF-DP measures	Yearly and end of study

Prevention effective continuation	# of women who don't miss any PrEP study visits/ total woman time reporting sexual activity in prior visit	Electronic provider log (REDCap)	Quarterly
Predictors of attrition at key steps in the PrEP cascade	Individual, pill/study and disease specific predictors of PrEP initiation, continuation and persistence	Study CRFs and in-depth interviews (month 7 and12) (mixed methods)	End of study
Healthcare provider attitudes and knowledge about PrEP in pregnancy	Provider knowledge about PrEP and barriers/facilitators to PrEP prescription in ante and postnatal care	In-depth interviews	Year 1 of study
HIV outcomes	HIV testing data: HIV-uninfected, HIV incidence in mother and child (if mother seroconverts) compared by PrEP use/non-use	Electronic provider log (REDCap)	End of study
Health outcomes and adverse events	Any side-effects, change in creatinine clearance, any negative maternal or neonatal outcomes (for mother and infant) compared by PrEP use/non-use	Electronic provider log (REDCap)	Weekly and quarterly
Infant growth outcomes	Measure infant weight, length, z-score and any adverse events in infants compared by PrEP use/non-use	Electronic provider log (REDCap)	Weekly and quarterly

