### **1. Determine the distribution of women across the PrEP cascade:**

- (1) Evaluate the proportion of pregnant and breastfeeding women who initiate PrEP out of all women offered PrEP**
- (2) Evaluate the proportion of pregnant and breastfeeding women who are retained in the PrEP cohort**
- (3) Evaluate the proportion of pregnant and breastfeeding women who initiate PrEP who adhere to PrEP using objective dried blood spot measures and subjective measures of self-reported pill count and adherence**
- (4) Evaluate the proportion of pregnant and breastfeeding women on PrEP (and not on PrEP) who acquire HIV, who transmit HIV to their infant, and who report adverse events**

- 2. Evaluate patient and provider-level factors associated with the PrEP cascade using quantitative and qualitative approaches (including in-depth interviews)**
- 3. Apply an established mathematical model to simulate the impact of improvement in the PrEP cascade on HIV infections averted (maternal and perinatal)**
- 4. Evaluate the effect of PrEP on vaginal microbiome in pregnant women and the consequent relationship to adverse pregnancy outcomes.**

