PrEP retention	# of women on PrEP who return for study visits (do not miss more than 1 visit) / total # of women in active cohort who are prescribed PrEP= proportion of women on PrEP who are retained in PrEP study	Electronic provider log (REDCap)	Daily, analysis weekly
PrEP adherence-subjective	# of women taking PrEP, who self-report taking their medication daily (& pill count to confirm this) during periods of sexual risk over time / total woman-time on PrEP in active cohort = PrEP adherence rate (subjective)	Electronic provider log (REDCap)	Daily, analysis weekly
PrEP adherence-objective	# of women taking PrEP who have >80% levels at >40ng/mL TDF-DP (indicating dosing in past 24 hours) at 3 rd trimester, delivery, and 6 weeks postpartum (and during sexual risk periods during that time) / total woman-time on PrEP in active cohort = PrEP adherence rate (objective)	Lab analysis of TDF-DP measures	Quarterly
Secondary Outcomes			
Predictors of attrition at key steps in the PrEP cascade	Individual, pill/study and disease specific predictors of attrition	Study survey	Study survey: Every study visit
HIV outcomes	HIV testing data: HIV-uninfected, HIV-positive for mother and child (if mother seroconverts)	Electronic provider log (REDCap)	Every visit
Health outcomes and adverse events	Any side-effects, creatinine, any negative maternal or neonatal outcomes (for mother and infant)	Electronic provider log (REDCap)	During routine lab tests and visits

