#### **Methods/Approach:**

- (1) **Primary outcome:** See **Table 1** for precise definitions of (1) PrEP initiation, (2) PrEP continuation, (3) PrEP persistence-subjective, and (4) PrEP persistence-objective
- (2) **Primary analysis:** Describe each outcome listed above via cumulative incidences at fixed intervals (e.g., cumulative PrEP initiation by delivery) and incidence densities over time. The general statistical approaches to these outcomes are analogous; data will be described graphically, including product-limit graphs, with preliminary analyses based on standard approaches for rates and proportions.
  - a. **PrEP initiation** will be modelled using a probit model (preferred to estimate risk factors for common outcomes) with individual-level covariates as fixed effects.
  - b. **PrEP continuation** will be examined using similar approaches; in addition, we will use time-to-event methods to estimate factors associated with time to loss (non-continuation) among women having initiated PrEP.
  - c. **PrEP persistence** will be modelled using mixed effects probit models as above and generalized estimating equations to examine the marginal effect of individual-level covariates on persistence during the study.
    - a. **Sub-group analysis:** we will analyze the primary outcomes by sub-groups including age (<25 and  $\geq$ 25 years), STI diagnosis, relationship status, pregnant/postpartum

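### SAP Table 1 defines both primary persistence measures as a count of women over woman-time on PrEP, and leaves the 'active cohort' under initiation and continuation undefined

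*Combined protocol and SAP*

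**What the plan says.** SAP section 2.4 sends the reader to Table 1 "for precise definitions of (1) PrEP initiation, (2) PrEP continuation, (3) PrEP persistence-subjective, and (4) PrEP persistence-objective".

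**Persistence.** In the objective row of Table 1, the numerator is the number of women on PrEP whose dried blood spot (DBS) reaches the threshold at third trimester, delivery and six weeks postpartum. The denominator and the name of the result read "total woman-time on PrEP in active cohort = PrEP persistence rate (objective". The self-report row uses the same denominator. Both adherence rows of protocol Table 2 have this form too; the objective one ends "total woman-time on PrEP in active cohort = PrEP adherence rate (objective". No time unit is given in either table.

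**Secondary measures.** Prevention-effective persistence is a count of women over woman-time with reported sexual activity. Prevention-effective continuation counts women who do not "miss any PrEP study visits/ total woman time reporting sexual activity in prior visit".

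**Initiation and continuation.** Initiation is the number "of women who initiate PrEP over time / total # of women in active cohort = proportion of women who initiate PrEP". The denominator of continuation is "total # of women in active cohort who are prescribed PrEP= proportion of women on PrEP who continue in PrEP study". Neither document defines 'active cohort'.

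**Elsewhere the plan uses women as the denominator, or a status.**
- Protocol objective 1(1): "Evaluate the proportion of pregnant and breastfeeding women who initiate PrEP out of all women offered PrEP". Objective 1(3) likewise asks for a proportion among initiators.
- SAP section 1, Study measures, item 3 defines persistence as a threshold status, with no woman-time.
- SAP section 2.2, item (4)(b) plans for 70% of those retained (n=378).
- The SAP section 4 shell on continuation and persistence shows self-reported persistence as n and % at each visit.

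**Related conflicts.** Continuation is a refill within 45 days in the Aim 1 list of SAP section 1, but not missing more than one visit in the rest of section 1 and in Table 1. Primary persistence uses all initiators under Missing data in SAP 2.4, but the analysis is based on 12-month completers under Sample size considerations in SAP section 1 and under Interpretation in SAP 2.4.

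**The concern.** Meeting a threshold at a visit is a status that can recur. It is not an event that accrues over time at risk. Dividing a count of women by woman-time therefore mixes units: the result is not a proportion, and it is not an incidence density because no event is defined. Its value depends on the unit chosen and falls as women use PrEP for longer, even if the share who are persistent does not change.

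These are primary outcomes of a study whose stated aim is the distribution of women across the PrEP cascade. An analyst who follows Table 1 literally would report a number that cannot be read as a step in that cascade or set against the planned 70%. The undefined 'active cohort' adds a second uncertainty. If it means women not lost or censored (an assumption), some continuation failures leave the denominator of the proportion meant to count them.

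**Working it through.** **1. The plan's own figures** (SAP section 2.2). 1200 × 0.60 = 720 initiators; 720 × 0.75 = 540 retained; 540 × 0.70 = 378 adherent. The chain reproduces exactly, and 378/540 = 70.0%.

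**2. Table 1's formula applied to the same women.** Value per woman-year = 378 / (540 × m/12), where m is mean months on PrEP (assumed; the plan gives no figure).

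| m | Woman-years | Table 1 value | Proportion persistent |
|---|---|---|---|
| 6 | 270 | 1.40 | 70% |
| 12 | 540 | 0.70 | 70% |
| 18 | 810 | 0.47 | 70% |

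The value can exceed 1, and here it matches the proportion only when mean use is exactly 12 months.

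**3. Time unit.** Suppose woman-time is limited to one quarter. The same women give 378/540 = 0.70 per woman-quarter, 378/(540 × 0.25) = 378/135 = 2.80 per woman-year, and 378/(540 × 3) = 378/1620 = 0.23 per woman-month. Only the woman-quarter matches 70%, and the table does not name it as the unit.

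**4. Window of the objective row.** The numerator is last read at six weeks postpartum, while follow-up runs to 12 months postpartum (protocol section 3). As worded, later time on PrEP adds to the denominator and cannot add to the numerator. The row also does not say whether a woman must reach the threshold at all three time points or at any one.

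**5. Which women, once woman-time is removed.** Among those retained, 378/540 = 70.0%. Among all initiators the share is (378 + 180p)/720, where p is the persistent share of the 180 not retained (assumed): 52.5% at p = 0, 70.0% at p = 0.7 and 77.5% at p = 1. This spread comes from the choice of denominator and from p, not from Table 1's formula. It shows only that the denominator must be named.

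**6. Continuation.** On all initiators, 540/720 = 75.0%. If a share f of the 180 non-retained leaves the 'active cohort' (assumed), the proportion is 540/(720 − 180f): 540/675 = 80.0% at f = 0.25, 540/630 = 85.7% at f = 0.5, and 100% in the extreme case f = 1.

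**The case against.** The strongest reply is that a proportion was plainly intended. SAP section 2.2 uses 720 of 1200, 540 of 720 and 378 of 540, which implies all enrolled women, all initiators and those retained as denominators. The Study measures text defines a status, the shell reports n and %, and the probit and generalized estimating equation models take a binary outcome. This stands: a reader might infer that the plan contains no proportion for persistence, and that is not so. But it shows that Table 1 conflicts with the rest of the SAP, and section 2.4 makes Table 1 the governing definition. The shell also has no DBS row, although DBS is the primary persistence measure, and it does not say whether its total is women ever or currently on PrEP.

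A reader might also infer that a woman who misses two consecutive quarterly visits automatically drops out of the denominator. The documents do not support this. The protocol's rule (section 4) counts clinical as well as study visits over more than 8 weeks and also requires that staff cannot trace her, or that she does not wish to continue. The SAP's rule (90 or more days) also requires that she cannot be contacted, and it sits in a monthly report template. A traceable woman who misses visits can remain a counted failure.

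It is also fair that the durations in step 2 are assumed, that a woman-quarter reproduces 0.70, and that no comparison between sites is planned. Finally, "we will use time-to-event methods to estimate factors associated with time to loss (non-continuation) among women having initiated PrEP" is a separate analysis that this point does not touch. The censoring weights and multiple imputation in SAP section 1 are useful, but they address missing data and do not repair a denominator in the wrong unit.

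**Conclusion.** The woman-time denominator is wrong as written in SAP Table 1 and protocol Table 2, for both primary persistence (adherence) measures. The secondary prevention-effective rows share the flaw. With 70% of 540 women persistent, the defined quantity is 1.40, 0.70 or 0.47 per woman-year at assumed durations of 6, 12 or 18 months, so it cannot answer objective 1(3). Because other sections already treat persistence as a status or a percentage, the final analysis may avoid the error. The defect is in the governing definition.

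'Active cohort' is undefined. The planning figures imply all enrolled women and all initiators, and the rise of continuation from 75% to 80% or 86% rests entirely on an assumed removal of lost women. The two continuation definitions and the two analysis sets are related conflicts to reconcile; the case against the woman-time denominator does not depend on them.

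**What to change.** In SAP Table 1 and protocol Table 2, define:

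- **Initiation:** women who ever started PrEP / all enrolled women offered PrEP.
- **Continuation:** women meeting the definition / all initiators, with the 45-day refill and missed-visit versions named as two separate outcomes.
- **Persistence at each scheduled assessment:** women meeting the threshold / all initiators due for that assessment. Count women known to have stopped PrEP as not persistent; this must be stated because DBS is taken only in women on PrEP (protocol section 5). Handle lost women and missing DBS by the weighting and imputation already in SAP section 1. Also report persistence among women currently on PrEP and retained, for comparison with the planned 70%, and keep the separate analysis of stoppage.
- **Prevention-effective persistence:** person-visits with sexual activity and the threshold met / person-visits with sexual activity.
- **Prevention-effective continuation:** scheduled visits attended / scheduled visits due, among those where sexual activity was reported at the prior visit.

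Remove 'active cohort' from these denominators. Reconcile the two loss-to-follow-up rules (protocol section 4 and the SAP monthly enrolment template). Do not restrict these outcomes to 12-month completers. Add DBS rows with stated denominators to the continuation and persistence shell in SAP section 4.

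The cost is wording and shell edits, with no new data. The downside is that some reported proportions may be lower.

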#### *Survey measures*

At study measurement visits, questionnaires will be administered to mothers participating in the study. Following standard procedures, the questionnaires will be translated into isiXhosa and Afrikaans and back translated to ensure appropriate phrasing. Questionnaires will include:

- Basic demographic information and obstetric history (enrollment only)
- Partner's HIV status
- Sexual behaviors in the past month and week including # of sex partners, type of sex, and frequency of sex and condom use
- Substance use information using the AUDIT-C and DAUDIT scales
- Risk perception scales
- Partner, community and social support for PrEP
- For PrEP users, questions related to PrEP adherence according to self-report (the 3-day and 1-month recall and a visual analog scale) and pharmacy-based pill counts will be conducted at each study measurement visit.

- Additional schedules will be used to collect data on symptoms in mothers that are potential side-effects of PrEP use (at all study visits)
- We will also use short questionnaires to collect data on all women's experiences in the study, and the acceptability of the PrEP initiation, including what kind of services were offered at each visit (e.g. counseling, peer mentorship, and IEC materials, medication)
- Self-reported symptoms related to STIs
- This will focus on the positive and negative aspects of their experiences of PrEP initiation in pregnancy and breastfeeding and any factors associated with PrEP initiation, retention, and adherence.

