- **Measurement of use of PrEP:** Conducted through alternate definitions of the main outcomes (e.g. persistence by self-report versus persistence by pharmacy refill), compared using measures of agreement and will be analyzed as independent models to contrast estimated associations.
- **Measurement of prevention-effective execution:** Execution refers to PrEP persistence during a time when at-risk sex happens. It is calculated by: number of doses reported, or recorded/number of expected doses based on HIV risk and PrEP initiation/discontinuation
- **Prevention-effective continuation:** Prevention-effective continuation describes the duration of PrEP use during periods of HIV risk and references the absolute time of use during pregnancy and breastfeeding periods. We will adapt the methodology from previous PrEP studies in SA including FEM-PrEP to create a semi-ordinal composite persistence score from blood specimens from DBS every 2-months.  
For *Aim 1*, each outcome will be described via cumulative incidences at fixed intervals (e.g., cumulative PrEP initiation by delivery) and incidence densities over time. The general statistical approaches to these outcomes are analogous; data will be described graphically, including product-limit graphs, with preliminary analyses based on standard approaches for rates and proportions.

For *Aim 1*, we will also describe the frequency of HIV outcomes, including maternal HIV acquisition and MTCT, and any laboratory or self-reported side effects (e.g. changes in creatinine or self-reported side-effects [GI symptoms, headache, and etc.]). Analyses will include pure-count and person-time approaches; for the latter, confidence intervals will be calculated following the method of Breslow and Day. We will also describe infant outcomes over time (including birthweight, gestational age at delivery, pregnancy loss and any infant illness, hospitalization or death). While we expect the frequency of adverse HIV-related outcomes to be low, we will

describe characteristics of women who did/did not acquire HIV, and consider further analyses using the approaches outlined above.

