**Methods/Approach:**

See **Table 1** for precise definitions of prevention effective PrEP continuation and persistence

- (1) *Secondary analysis:* Describe each outcome listed above via cumulative incidences at fixed intervals (e.g., cumulative PrEP continuation after 1 year in study) and incidence densities over time. The general statistical approaches to these outcomes are analogous to the primary outcomes (above). Data will be described graphically, including product-limit graphs, with preliminary analyses based on standard approaches for rates and proportions.
- (2) Other analysis approaches on the PrEP cascade:
  - a. When time-dependent or visit-specific covariates are included in the analysis of cumulative PrEP initiation we will shift to a mixed-effects setting with random effects around individual participants.

Other outcomes (secondary outcomes):

- a. **Predictors of attrition at key steps in the PrEP cascade:** Methods will involve mixed methods analysis. Utilizing the qualitative data from the IDIs at month 7 and 12 of the study from a random selection of 60 participants (30 randomly selected from those who initiated PrEP and 30 randomly selected from those who chose not to initiate) to complement the quantitative data to understand factors associated with PrEP persistence and non-persistence, including 1) individual factors, (including risk perception, sexual activity and risk, substance use, and partner/family/community discouragement), 2) the pill regimen (side effects and concerns about adverse pregnancy or infant outcomes) AND patient-provider relationship and 3) the disease-related factors (including reasons behind stigma associated with PrEP taking).
  - i. **Individual factors:** Collected from CRFs in all participants (regardless of PrEP uptake) including: risk perception, sexual activity and risk, substance use, partner/family/community discouragement, sociodemographic variables, relationship characteristics and fear about adverse pregnancy and/or infant health outcomes. Collected from the sub-set of women participating in the IDIs.
  - ii. **Pill/study factors:** Collected from CRFs in participants who decide to take PrEP, including: side effects on PrEP, and barriers to attending frequent study visits and DBS during those visits, and provider participant communication and support

(measured from participant perspective). Collected from the sub-set of women participating in the IDIs.

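### SAP Table 1's subjective prevention-effective persistence measure puts all persistent women, sexually active or not, over sexually active woman-time only, so it rises as sexual activity falls

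*Combined protocol and SAP*

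**What the plan says.** SAP section 2.5 (Secondary analyses) points to SAP Table 1 (Study measures for PrEP-PP for AIM 1) "for precise definitions of prevention effective PrEP continuation and persistence". Three rows matter.

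- **Persistence, subjective:** the number "of women reporting adherence to PrEP (as per PrEP persistence subjective measure)/ total woman-time reporting sexual activity in past 30 days". The borrowed measure is the primary subjective row, met by PrEP use on ≥5 of the last 7 days or on ≥25 of the last 30. That primary row does limit its denominator to time on PrEP: "out of last 30 days (self-reported)/ total woman-time on PrEP in active cohort = PrEP persistence rate (subjective".
- **Persistence, objective:** the number "of women having TDF-DP in DBS (as per PrEP persistence objective measure)/ total woman-time reporting sexual activity in past 30 days". The borrowed objective row carries a qualifier: "and during sexual risk periods during that time) / total woman-time on PrEP in active cohort = PrEP persistence rate (objective".
- **Continuation:** the number "of women who don't miss any PrEP study visits/ total woman time reporting sexual activity in prior visit".

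The intent is stated in three places. The SAP's statistical considerations for Aims 1 and 2 explain prevention-effective persistence as persistence at times of sexual activity. The SAP's Study measures section and the purpose of section 2.5 express the same idea in terms of sexual risk. A separate execution measure, doses taken over doses expected given HIV risk, is also described: "Execution refers to PrEP persistence during a time when at-risk sex happens". The protocol survey (section 5, Survey measures) collects "Sexual behaviors in the past month and week including # of sex partners, type of sex, and frequency of sex and condom use".

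**The concern.** In the subjective row, a woman who takes PrEP daily and reports no sex adds one to the numerator and nothing to the denominator. A drop in sexual activity, for example around delivery, would then read as better protection with no change in pill-taking.

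This could also mislead group comparisons. SAP section 2.4 names pregnant/postpartum and relationship status as subgroups for the primary outcomes, and section 2.5 calls the secondary approach analogous. If sexual activity differs between such groups, the measure differs too, and the group having less sex looks better covered.

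There is a second problem in the same row. Its PrEP rule can be met on a 7-day window alone, while sexual activity is taken over 30 days. The SAP expects women to stop and restart PrEP, so a recent restart can be credited to sex that came before it.

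**Working it through.** **Inputs.** From the SAP (sample size section and section 2.2): 1200 enrolled, 60% initiating, 75% of those continuing, 70% of those adherent during at-risk periods. The share *s* of woman-visits reporting sex in the past 30 days is not given, so it is varied as an assumption.

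**1. The plan's own figure.** 1200 × 0.60 = 720; 720 × 0.75 = 540; 540 × 0.70 = 378. This reproduces the SAP's 378. It is a proportion of women (0.70). No expected value is given for the Table 1 ratios.

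**2. The Table 1 ratio.** Take one 30-day unit per woman-visit and persistence *p* that does not depend on sex. The row as written gives *p*/*s*. The intended quantity, persistence among the sexually active, is *ps*/*s* = *p*.

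- PrEP users only, *p* = 0.60: ratio 0.60/*s*.
- PrEP users only, the plan's numbers: ratio 378/(540*s*).
- Non-users also in the denominator, with 60% initiating: 0.60 × 0.60 = 0.36, ratio 0.36/*s*.

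| *s* | 0.60/*s* | 378/(540*s*) | 0.36/*s* |
|---|---|---|---|
| 0.8 | 0.75 | 0.875 | 0.45 |
| 0.6 | 1.00 | 1.17 | 0.60 |
| 0.5 | 1.20 | 1.40 | 0.72 |
| 0.4 | 1.50 | 1.75 | 0.90 |
| True value at every *s* | 0.60 | 0.70 | 0.36 |

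Each column is its true value divided by *s*. Two groups with identical 60% persistence, 80% and 40% sexually active, would show 0.75 and 1.50. That is a two-fold difference, the size of the relative risk of 2.0 used in the sample-size section.

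**3. Persistence that depends on sex.** If 50% of active and 75% of inactive women persist, the ratio is (0.50*s* + 0.75(1 − *s*))/*s*: 0.69, 1.00 and 1.63 at *s* = 0.8, 0.6 and 0.4, against a true 0.50.

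**4. The time unit.** Restricting the numerator alone does not give a proportion. A value of 0.70 per 30-day woman-month is 0.70 × 365.25/30 = 8.52 per woman-year. If each woman is counted once while time accrues over 6 visits (assumed), 378/(540 × *s* × 6) is 0.15 at *s* = 0.8 and 0.29 at *s* = 0.4.

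**5. The windows.** A woman with 5 doses in the last 7 days, none on days 8–30, and sex only on days 8–30 meets the rule. She took 5/30 = 17% of the month's doses, all after the risk. The other option requires at least 25/30 = 83% and matches the 30-day window.

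**The case against.** The strongest reply is that the intent is clear in the narrative, that the execution measure is already tied to risk, and that this is a gap in table wording for secondary, largely descriptive outcomes with no decision threshold. The point about weight stands. The rest does not remove the problem, because section 2.5 makes Table 1 the operative definition and its subjective row does not carry the restriction. The protocol's Table 2 does tie its subjective adherence row to periods of sexual risk.

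Three stronger readings are tempting, and the documents do not support them.

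- **A reader might infer that values above 1 prove the mismatch.** A count over woman-time is a rate and has no ceiling of 1, even with a matched numerator. The values above 1 also assume PrEP users only and one unit per woman-visit, neither of which the row states. With non-users included, none of the four illustrative values exceeds 1. On the plan's 378/1200 = 0.315, the ratio exceeds 1 only when *s* is below 0.315.
- **A reader might infer that the objective row has the same fault.** Its borrowed measure mentions sexual risk periods, so its numerator is ambiguous rather than plainly unrestricted. A blood-spot level also has no recall window to mismatch.
- **A reader might infer that the continuation row judges an interval by sexual activity lying wholly outside it.** The row states no recall period, does not say whether missed visits are counted for one interval or cumulatively, and measures attendance rather than dosing. Taking sexual activity from the prior visit is defensible because it classifies women before their attendance is known. Taking it from the visit that closes the interval would be worse: only attenders could be classified, and continuation would be 100% by construction.

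**Conclusion.** The subjective prevention-effective persistence row does not measure what the SAP says it should. Its value is inflated by 1/*s* when persistence is unrelated to sex, that is, by 1.25 to 2.5 times for *s* from 0.8 to 0.4. The direction follows from the definition. The size rests on the assumed *s* and on one 30-day unit per woman-visit. The absolute values also depend on whether non-users are in the denominator, which the row leaves open. The 7-day option separately credits dosing that follows the risk.

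The objective row needs clarifying. The continuation row shares the unrestricted numerator, but its use of the prior visit can stay. The primary outcomes do not depend on these rows, so this should be corrected before analysis but does not threaten the study's main results.

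**What to change.** Redefine the rows in SAP Table 1 as proportions of woman-visits, with clustering by woman. Use one restricted set for numerator and denominator, and state whether that set is limited to women on PrEP.

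- **(a)** PrEP on ≥5 of the last 7 days, among visits reporting sex in the past week.
- **(b)** PrEP on ≥25 of the last 30 days, among visits reporting sex in the past month.
- **(c)** Blood-spot level at or above the SAP threshold, among visits reporting sex in the past month.
- **(d)** Continuation: keep sexual activity from the prior visit, restrict the numerator to those same women, and describe the result as attendance after reported risk, not as PrEP coverage of that risk.

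Report (a) and (b) separately rather than joined by an either/or rule.

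The cost is table wording and minor programming. Past-week and past-month sexual behaviour is in the protocol survey, and 7-day and 30-day PrEP recall is in the SAP's Study measures section and report templates. The protocol's survey list names 3-day and 1-month PrEP recall, so confirm that the 7-day item is on the form. The downside is fewer visits in measure (a). These measures match windows; they do not date doses against individual sex acts.
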